7.5 Adjustments for Multiple Comparisons

No multiplicity adjustments will be considered in this study.

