Safety Assessments	
This is a prospective, randomized, controlled study where the only change in routine management is the placement of the BIS™ monitor probe on the forehead. The choice of sedative drugs, dose, and route of administration will be based on clinical indications as judged by the attending Anesthesiologist, and it will not be changed for the study.
 
The BIS™ monitor will not be used in situations where the placement of the probe will interfere with a procedure, cause scan artifacts, or where the presence of a metal monitor is contraindicated (e.g., MRI scans). Therefore, we believe there is only a minimal increase in risks from participating in the study. This risk relates to the possibility of developing irritation to the skin at the site of placement.

	
Subjects will be monitored for Adverse Events, Serious Adverse Events, and Device-Related Adverse Events from BIS™ sensor applications throughout the BIS™ sensor removal.

Statistics	
Standard demographic information and baseline characteristics will be summarized using descriptive statistics. For safety assessments, adverse events (AEs) will be summarized using frequency counts and percentages. Descriptive statistics will be provided by severity and relationship as needed.
 
The primary analysis will be based on all evaluable data (excluding training subjects). Normality of data will be tested using the Kolmogorov-Smirnov test. Depending on whether normality assumption hold, a two group t-test or Wilcoxon rank-sum test will be used to compare between the two treatment groups. A P-value of less than 0.05 is considered statistically significant unless otherwise specified.
 
The secondary endpoints will be evaluated using the Holm-Bonferroni method to ensure the overall type I error rate is controlled at the 0.05 level.
 
Cardiovascular Variables will be summarized for both groups. The incidence of hypotension will be summarized and compared to anesthesia sedation levels.
 
The anesthetic requirements with the BIS™ value, the percentage of time during maintenance with BIS™ values within the specified ranges, and number of episodes and duration of burst suppression will be assessed for both treatment groups.
 
Additional endpoints, including PAED scale, Pain Rating Score and a subgroup analysis for subjects requiring neuromuscular blockade, will be summarized using descriptive statistics for each group and groups combined.

4. Introduction

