14.1 General Aspects of Analysis

Standard demographic information and baseline characteristics will be summarized using descriptive statistics. For safety assessments, adverse events (AEs) will be summarized using frequency counts and percentages. Descriptive statistics will be provided by severity and relationship as needed.

The primary endpoint will be collected as a continuous variable every minute along with the BIS values. The primary analysis will be based on all evaluable data (excluding training subjects). Normality of data will be tested using the Kolmogorov-Smirnov test. Depending on whether normality assumption holds, a two-group t-test or Wilcoxon rank-sum test will be used to compare between the two treatment groups. A *P*-value of less than 0.05 is considered statistically significant unless otherwise specified.

The training subjects will not be included in the analysis set for the primary and secondary endpoints. The training subjects will be summarized descriptively and separately. Any specific findings from these subjects will be noted and discussed in the study report.

The following secondary endpoints will be evaluated:

- Time to first response (emergence)
- Time to PACU discharge readiness using Modified Aldrete Score
- Time to extubation

Upon meeting the primary endpoint, the secondary endpoints will be evaluated using the Holm-Bonferroni method. The method is a sequentially rejective multiple test procedure used to adjust multiplicity and to ensure the overall type I error rate is controlled at the 0.05 level. For statistical inferences, categorical variables will be evaluated using the Chi-square test or Fisher's exact test, and continuous variables will be evaluated using the t-test or Wilcoxon rank-sum test as appropriate. The analysis details will be clearly specified in the Statistical Analysis Plan.

Data Poolability

The clinical study will be conducted under a common protocol for each investigational site with the intention of pooling the data for analysis. Every effort will be made to promote consistency in study execution at each study site.

An assessment of data poolability of the sites will be performed using a mixed-effect model for the primary endpoint. A significance level of 0.15 will be considered. Sites with fewer than five subjects will be combined into large sites to ensure statistical robustness.

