If the sites are found to be significantly heterogeneous with respect to the primary endpoint, additional analyses will be conducted to further assess differences between sites in baseline and procedural variables that might contribute the differences.

Medtronic Business Restricted

Missing Data

The primary analysis will include all evaluable data and missing values will not be imputed. BIS™ values that are outside of the specified range of 45 – 60 during maintenance of anesthesia for >35% of the maintenance duration will be considered a protocol deviation and will result in an exclusion of the subject from the primary analysis. The excluded subject will be replaced, and data from all excluded subjects will be noted and discussed in the final study report. Additionally, sensitivity analysis (e.g., multiple imputation) may be performed as appropriate to assess the robustness of study results.

Additional Summaries and Considerations

Cardiovascular variables will be summarized for both treatment groups. The incidence of hypotension will be summarized and compared to anesthesia sedation levels.

The anesthetic requirements with the BIS™ value, the percentage of time during maintenance with BIS™ value within the specified ranges, and number of episodes and duration of burst suppression will be assessed for the BIS and SP groups.

Additional endpoints, including the PAED scale, PACU discharge readiness and a subgroup analysis for subjects requiring neuromuscular blockade, will be evaluated by using descriptive statistics and compared between both groups.

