16.6. CIP Amendments

The Investigator may propose any appropriate modification(s) to the Clinical Investigation Plan. Medtronic will review and decide whether the modification(s) will be implemented.

Medtronic will submit any amendment to the Clinical Investigation Plan, including a justification for such amendment, to the investigators to obtain approval from their IRB.

Any amendment to the protocol requires written approval by the IRB and regulatory authority (if applicable) prior to its implementation unless there are overriding safety reasons. In some instances, an amendment may require a change to the ICF.

The Sponsor and Investigator will obtain IRB approval concerning the revised ICF prior to the implementation of the change. The Investigator understands that subjects must be consented using the most current IRB approved version of the ICF. If the ICF is updated, subjects who have participated will be re-consented at the direction of the IRB.

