7.9 Evaluation of Objectives

Standard demographic information and baseline characteristics will be summarized using descriptive statistics. For safety assessments, adverse events (AEs) will be summarized using frequency counts and percentages. Descriptive statistics will be provided by severity and relationship as needed.

The primary endpoint will be collected as a continuous variable every minute along with the BIS™ values. The primary analysis will be based on all evaluable data (excluding training subjects). Normality of data will be tested using the Kolmogorov-Smirnov test. Depending on whether normality assumption holds, a two-group t-test or Wilcoxon rank-sum test will be used to compare between the two

treatment groups. A P-value of less than 0.05 is considered statistically significant unless otherwise specified.

The mean BIS™ and standard deviation will be determined at each concentration of sevoflurane. A semi-logarithmic plot of sevoflurane concentration versus BIS™ will be provided, and the correlation will be quantified by using an inhibitory sigmoid E_{max} model (Denman et al., 2000) on steady state points. The model is formulated as:

$$E = E_0 - \frac{(E_{max})(C^\gamma)}{EC_{50}^\gamma + C^\gamma}$$

As noted by Denman, the E_0 is specified to be 100, γ (gamma) is the scale factor, and E_{max} is the maximal effect constrained to 100. The EC_{50} is the sevoflurane concentration corresponding to the half-maximal effect (e.g., BIS™ of 50), and this value will be estimated, along with 95% confidence intervals, for each age group.

The training subjects will not be included in the analysis set for the primary and secondary endpoints. The training subjects will be summarized descriptively and separately. Any specific findings from these subjects will be noted and discussed in the study report.

The following secondary endpoints will be evaluated:

- Time to first response (emergence)
- Time to PACU discharge readiness using Modified Aldrete Score
- Time to extubation.

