Upon meeting the primary endpoint, the secondary endpoints will be evaluated using the Holm-Bonferroni method. The method is a sequentially rejective multiple test procedure used to adjust multiplicity and to ensure the overall type I error rate is controlled at the 0.05 level. For statistical inferences, categorical variables will be evaluated using the Chi-square test or Fisher's exact test, and continuous variables will be evaluated using the t-test or Wilcoxon rank-sum test as appropriate.

Cardiovascular variables will be summarized for both treatment groups. The incidence of hypotension will be summarized and compared to anesthesia sedation levels.

The anesthetic requirements with the BIS™ value, the percentage of time during maintenance with BIS™ value within the specified ranges, and number of episodes and duration of burst suppression will be assessed for the BIS and SP groups.

Additional endpoints, including the PAED scale, PACU discharge readiness, Anesthesia Airway Management, and a subgroup analysis for subjects requiring neuromuscular blockade, will be evaluated by using descriptive statistics and compared between BIS and SP groups.

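### SAP 7.5 rules out any multiplicity adjustment, while SAP 7.9 and Protocol 14.1 require Holm-Bonferroni at overall 0.05 for three secondary endpoints; the secondary list itself also needs reconciling

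*SAP*

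**What the plan says.** **The bar on adjustment.** SAP 7.5, the section given over to multiple comparisons, consists of one sentence: "No multiplicity adjustments will be considered in this study". It is not limited to particular endpoints.

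**The requirement to adjust.** SAP 7.9 introduces a list with "The following secondary endpoints will be evaluated" and names three: time to first response (emergence), time to PACU discharge readiness by Modified Aldrete Score, and time to extubation. It continues: "Upon meeting the primary endpoint, the secondary endpoints will be evaluated using the Holm-Bonferroni method". Protocol 14.1 has the same list, gate and method, and describes the method as "used to adjust multiplicity and to ensure the overall type I error rate is controlled at the 0.05 level". The Statistics row of the protocol synopsis agrees, without mentioning the gate: "The secondary endpoints will be evaluated using the Holm-Bonferroni method to ensure the overall type I error rate is controlled at the 0.05 level".

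**The secondary list elsewhere.** The endpoint row of the synopsis gives the secondary recovery assessments as emergence, PACU discharge readiness and Anesthesia Airway Management (awake or deep extubation, airway reflexes). Protocol 5.2.2 and the Endpoints section of the SAP carry the same recovery items. None of the three names time to extubation.

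**The additional endpoints.** SAP 7.9 later lists "Additional endpoints, including the PAED scale, PACU discharge readiness, Anesthesia Airway Management, and a subgroup analysis for subjects requiring neuromuscular blockade". The corresponding list in Protocol 14.1 reads "Additional endpoints, including the PAED scale, PACU discharge readiness and a subgroup analysis for subjects requiring neuromuscular blockade". Both lists are to be summarised descriptively and compared between groups, with no test named.

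**The concern.** An analyst who follows SAP 7.5 and one who follows SAP 7.9 can report different secondary findings from the same data. Take a secondary p-value of 0.03. Under 7.5 it is significant. Under Holm with three endpoints it fails if it is the smallest of the three (threshold 0.0167) or the second smallest (0.025). It passes only as the largest, after the other two have passed.

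No order of precedence between the two SAP sections is stated. Protocol section 14 sends the reader to the SAP for the analysis, and 14.1 says the details will be specified there, so the protocol does not resolve a conflict inside the SAP. SAP section 3 also describes its methods as flexible. Either rule could therefore be chosen after results are known and defended from the plan. The synopsis calls the study pivotal, and SAP section 3 foresees use of the analyses in regulatory submissions, so the secondary claims matter.

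The membership of the family matters as well, because Holm's thresholds depend on how many endpoints are in it.

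**Working it through.** **Inputs.** Three secondary endpoints, two-sided 0.05 per test and overall 0.05 (SAP 7.9, Protocol 14.1). Recovery times for ages 3–18 (Protocol 4.1.3.2, recovery-time Table 3). The documents give no correlation between the endpoints, so a range is assumed.

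**1. Reproduce the plan's 0.05.** Holm with three endpoints compares the ordered p-values with 0.05/3 = 0.0167, 0.05/2 = 0.025 and 0.05. The bound is 3 × 0.0167 = 0.05, as stated. With independent endpoints and all three nulls true, the error is 1 − (1 − 0.05/3)³ = 0.049.

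**2. The same family under SAP 7.5.** Each endpoint is tested at 0.05. If independent, 1 − 0.95³ = 0.143. Upper bound: 3 × 0.05 = 0.15.

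**3. Correlated endpoints.** Simulation of equicorrelated normal test statistics, at least 1,000,000 draws (simulation error about 0.1 point), primary gate passed, all three secondary nulls true:

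| Assumed correlation | No adjustment | Holm |
|---|---|---|
| 0 | 14.3% | 4.9% |
| 0.3 | 13.6% | 4.7% |
| 0.5 | 12.5% | 4.5% |
| 0.7 | 10.9% | 3.9% |
| 0.8 | 9.8% | 3.5% |
| 0.9 | 8.4% | 3.0% |

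**4. Two of the three nulls true.** Without adjustment: 9.8%, 9.1% and 7.8% at correlations 0, 0.5 and 0.8 (exact at 0: 1 − 0.95² = 0.0975). With Holm: at most 5%.

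**5. Primary null also true.** The gate then limits the error even without adjustment. At independence it is 0.05 × 0.143 = 0.007. At correlations 0.5 and 0.8 among all four tests it is 2.0% and 3.4%. The loss of control therefore arises when the primary effect is real, which is the case the trial is designed for.

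**6. What Holm costs.** Standardised differences from Table 3 (SP versus BIS), using d = difference / √((SD₁² + SD₂²)/2):

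- First response: (7.0 − 4.2)/√((3.9² + 3.7²)/2) = 2.8/3.80 = 0.737
- Extubation: (11.3 − 7.1)/√((5.9² + 3.7²)/2) = 4.2/4.92 = 0.853
- Ready to discharge: (26.7 − 20.0)/√((11.2² + 7.9²)/2) = 6.7/9.69 = 0.691

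Power from the noncentral t (unadjusted) and simulation (Holm, correlations 0 to 0.8), with 54 per arm (108/2) assumed:

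| Endpoint | Unadjusted | Holm |
|---|---|---|
| First response | 96.7% | 95.0–96.4% |
| Extubation | 99.2% | 98.1–99.1% |
| Ready to discharge | 94.5% | 93.3–94.2% |

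The loss is about 0 to 2 points. With 18 per arm (testing within an age group), unadjusted power is about 57%, 70% and 52%, and with Holm about 46–47%, 56–58% and 42–44%: a loss of roughly 9 to 14 points.

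**The case against.** **The intended rule is easy to recover.** Holm-Bonferroni appears in the synopsis, Protocol 14.1 and SAP 7.9, with method and overall level each time. SAP section 3 says the SAP elaborates the protocol's analyses. The 7.5 sentence is generic and sits in a SAP with unfilled template instructions (7.1.2, 7.7), so it may be a leftover. This supports choosing the 7.9 rule as the correction. It does not make the conflict harmless, because the origin of the sentence is an inference and 7.5 is where a reader would look for the multiplicity rule.

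**14% is the unfavourable end.** That stands. Three recovery times from the same child are unlikely to be independent, and at a correlation of 0.8 to 0.9 the figure is about 8% to 10%. It also requires that no recovery time differs, whereas the earlier study in ages 3–18 reported differences in all three. Even so, every value in the range is above the stated 0.05.

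**The family is not settled by 7.9 alone.** This also stands. Airway management is secondary in the synopsis and additional in SAP 7.9, and time to extubation appears as a secondary endpoint only in 14.1 and 7.9. Correcting 7.5 without addressing this would settle the question silently.

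**PACU discharge readiness.** A reader might infer that a Holm endpoint has been demoted to a descriptive one. The text does not support that. The additional lists omit the words *time to*, they call for a comparison as well as a description, and Protocol 10.9.6 separately records Modified Aldrete scores. The second mention may mean the score. It needs clarifying, and deleting it could remove a planned summary.

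**Conclusion.** The contradiction is real and lies in current text, both within the SAP and between SAP 7.5 and the protocol. It should be resolved before results are seen, because it can change which secondary claims are declared.

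Following 7.5 with a true primary effect and all three secondary nulls true gives a family-wise error of about 8% to 14% (bound 15%) instead of at most 5%. This rests on a family of three, normal test statistics and the assumed correlations of 0.9 to 0.

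A reader might infer that the trial's overall error rate is inflated, or that the sample size is wrong. Neither follows. The primary test is not affected, the sample size rests on the primary endpoint only, and when the primary null is true the gate alone keeps the secondary error at or below 5%.

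The power cost is only illustrative. It assumes that all 108 subjects contribute to each endpoint, although extubation is recorded as applicable. It also assumes roughly normal times, and the earlier patients had tonsillectomy and/or adenoidectomy with nitrous oxide.

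**What to change.** 1. Replace the SAP 7.5 sentence with the rule already in 7.9 and 14.1, for example: *Once the primary endpoint is met, time to first response (emergence), time to PACU discharge readiness and time to extubation are tested by Holm-Bonferroni at an overall two-sided level of 0.05. Other comparisons are unadjusted.*
2. In the same edit, reconcile the secondary list. Give Anesthesia Airway Management one status, and either name time to extubation as secondary in the endpoint sections (synopsis, Protocol 5.2.2, SAP Endpoints) or explain why it appears only in the analysis sections. If the family changes from three, restate the Holm thresholds.
3. In the additional-endpoint lists of SAP 7.9 and Protocol 14.1, say whether PACU discharge readiness means the Modified Aldrete score, as a descriptive summary, or the time endpoint already in the Holm family.

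**Cost.** A wording change to the SAP, with no new data and no change in sample size. It brings 7.5 into line with existing protocol text. The protocol edits can wait for the next amendment, since Protocol 16.6 says: "Any amendment to the protocol requires written approval by the IRB and regulatory authority (if applicable) prior to its implementation". The power cost is about 0 to 2 points if the secondary tests pool the age groups, and larger if they are done within them.

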7.6 Demographic and Other Baseline Characteristics

Subject demographics, medical history will be summarized using descriptive statistics for continuous variables (mean, standard deviation, number of observations, minimum and maximum) and frequency tables for discrete variables.

Baseline demographic data will be summarized and reported in a table entitled “Summary of Subject Demographics”. This table summarizes the subject population with respect to age (in years) at entry into the study, gender. Age will be summarized using descriptive statistics: n, arithmetic mean, standard deviation, median, and range. Subjects with missing data that cannot be resolved prior to database lock will not be included in the tabulation and excluded from the summary statistics; Gender will be summarized using counts and percentages. In addition to the reported values, unknown or unreported values will also be reported. The supportive data for the demographics table will be presented in a listing.

7.7 Treatment Characteristics

Surgical procedure characteristics and exposure to study product will be summarized using descriptive statistics. Describe how concomitant therapies and medications will be summarized using descriptive statistics.

7.8 Interim Analyses

No interim analyses are planned for this study.

7.9 Evaluation of Objectives

Standard demographic information and baseline characteristics will be summarized using descriptive statistics. For safety assessments, adverse events (AEs) will be summarized using frequency counts and percentages. Descriptive statistics will be provided by severity and relationship as needed.

The primary endpoint will be collected as a continuous variable every minute along with the BIS™ values. The primary analysis will be based on all evaluable data (excluding training subjects). Normality of data will be tested using the Kolmogorov-Smirnov test. Depending on whether normality assumption holds, a two-group t-test or Wilcoxon rank-sum test will be used to compare between the two

treatment groups. A P-value of less than 0.05 is considered statistically significant unless otherwise specified.

The mean BIS™ and standard deviation will be determined at each concentration of sevoflurane. A semi-logarithmic plot of sevoflurane concentration versus BIS™ will be provided, and the correlation will be quantified by using an inhibitory sigmoid E_{max} model (Denman et al., 2000) on steady state points. The model is formulated as:

$$E = E_0 - \frac{(E_{max})(C^\gamma)}{EC_{50}^\gamma + C^\gamma}$$

As noted by Denman, the E_0 is specified to be 100, γ (gamma) is the scale factor, and E_{max} is the maximal effect constrained to 100. The EC_{50} is the sevoflurane concentration corresponding to the half-maximal effect (e.g., BIS™ of 50), and this value will be estimated, along with 95% confidence intervals, for each age group.

The training subjects will not be included in the analysis set for the primary and secondary endpoints. The training subjects will be summarized descriptively and separately. Any specific findings from these subjects will be noted and discussed in the study report.

The following secondary endpoints will be evaluated:

- Time to first response (emergence)
- Time to PACU discharge readiness using Modified Aldrete Score
- Time to extubation.

Upon meeting the primary endpoint, the secondary endpoints will be evaluated using the Holm-Bonferroni method. The method is a sequentially rejective multiple test procedure used to adjust multiplicity and to ensure the overall type I error rate is controlled at the 0.05 level. For statistical inferences, categorical variables will be evaluated using the Chi-square test or Fisher's exact test, and continuous variables will be evaluated using the t-test or Wilcoxon rank-sum test as appropriate.

Cardiovascular variables will be summarized for both treatment groups. The incidence of hypotension will be summarized and compared to anesthesia sedation levels.

The anesthetic requirements with the BIS™ value, the percentage of time during maintenance with BIS™ value within the specified ranges, and number of episodes and duration of burst suppression will be assessed for the BIS and SP groups.

Additional endpoints, including the PAED scale, PACU discharge readiness, Anesthesia Airway Management, and a subgroup analysis for subjects requiring neuromuscular blockade, will be evaluated by using descriptive statistics and compared between BIS and SP groups.

